## 3.2 Trial Plan

### ***Enrollment***

A total of approximately 140 participants in Stage I and 700 participants in Stage II will be enrolled. Eligible participants will be identified and recruited, in accordance with inclusion / exclusion criteria. Each participant's parent / guardian must sign and date the ICF before any procedure or treatment associated with the study is performed. A step-down approach to vaccine administration from Stage I to Stage II will be used: toddlers will first be vaccinated (Stage I) and after the safety data of at least █% of participants from Stage I has been reviewed by the SMT and by the independent DMC, the enrollment of infants will start. It is to be noted that after Stage I data review, the DMC may recommend dropping one or more SP0202 formulations before

‡ For both toddlers and infants, anaphylaxis/hypersensitivity, convulsions (including febrile convulsions), hypotonic-hyporesponsive episode, and apnea will be considered as AESIs.

\* Not applicable from protocol V5.0

moving to Stage II. In any cases, the sample size of each group will remain unchanged (ie, around 175 infants per group) and ratio between groups will be balanced.

### Vaccination

In Stage I, toddlers aged between 12 to 15 months, will receive one dose of either one formulation of SP0202 formulation or Prevnar 13, concomitantly administered with Pentacel.

In Stage II, infants aged 2 months will receive 3 doses of either one SP0202 formulation or Prevnar 13 approximately at 2, 4, and 6 MoA and a 4th dose at 12 to 15 MoA (Groups 5, 6, 7, and 8), co-administered with pediatric vaccines recommended at this age.

All infants will receive the following routine vaccines (summarized in [Table 3.2](#)):

- Pentacel (DTaP-IPV//Hib) at 2, 4, 6 months of age. It is to be noted that the fourth Pentacel dose will be given after the completion of the last study visit. The study personnel / Investigator will be responsible for administering this dose at the recommended age as per their standard practices
- RotaTeq (pentavalent rotavirus vaccine [RV5]) at 2, 4, and 6 months of age
- M-M-RII (measles, mumps, rubella [MMR] vaccine) at 12 to 15 months of age
- VARIVAX (varicella vaccine) at 12 to 15 months of age
- In addition to routine vaccine mentioned above, hepatitis B vaccination (ENGERIX-B) can be administered concomitantly with Pentacel and PCV doses at V01, V02, and V03. A first dose of hepatitis B vaccine can be given at least 28 days prior to study enrollment.

**Table 3.2: Injection schedule for study and pediatric vaccines in infants**

Visit (V)	V01	V02	V03	V05
Approximate age (months)	2	4	6	12 to 15
PCV for Group 5, 6, and 7	SP0202 (IIb, VI, or VII)			
Group 8	Prevnar 13	Prevnar 13	Prevnar 13	Prevnar 13
Concomitant pediatric vaccines	Pentacel* RotaTeq†	Pentacel* RotaTeq†	Pentacel* RotaTeq†	M-M-R II + VARIVAX§
	ENGERIX-B‡	ENGERIX-B‡	ENGERIX-B‡	

\* Pentacel (Diphtheria and Tetanus Toxoids and Acellular Pertussis Adsorbed, Inactivated Poliovirus and *Haemophilus b* Conjugate [Tetanus Toxoid Conjugate]; Sanofi Pasteur Ltd)

† RotaTeq (Rotavirus Vaccine, Live, Oral, Pentavalent); Merck & Co, Inc.

‡ ENGERIX-B (Purified Recombinant Hepatitis B Surface Antigen; GlaxoSmithKline Inc.). Hepatitis B vaccination can be administered concomitantly with Pentacel and PCV doses at V01; V02 and V03. A first dose of hepatitis B vaccine can be given at least 28 days prior to study enrollment.

§ M-M-RII (Measles, Mumps, and Rubella Virus Vaccine Live) and VARIVAX® (Varicella Virus Vaccine Live); Merck & Co, Inc.

Additionally, based on the immunogenicity results, a rescue dose of Prevnar 13 will be recommended for any participant that will receive one of the 3 formulations of SP0202 vaccine and that will meet the following criteria:

- Any toddler in Stage I of the study with serotype specific pneumococcal IgG antibody concentration < 0.35 µg/mL for 4 or more serotypes in common between SP0202 vaccine and Prevnar 13 at 1-month post-vaccination.
- Any infant in Stage II of the study with serotype specific pneumococcal IgG antibody concentration < 0.35 µg/mL for 4 or more serotypes in common between SP0202 vaccine and Prevnar 13 at 1-month post-dose 3.

The rescue dose of Prevnar 13 should be given as soon as possible after the immunogenicity results will be available for toddlers, or as soon as possible after the immunogenicity results of the fourth dose of SP0202 vaccine for infants. This rescue dose will be given outside of the protocol visit.

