- 4) Obtain the blood sample (BL0002 – 6 mL) (see [Section 7.1](#) for detailed instructions regarding the handling of blood samples).
If the blood sample cannot be obtained, the parent/guardian should be given the opportunity to bring the subject back to the study site for another attempt, as long as the subject continues to remain eligible for the study. All attempts should be made to obtain a blood sample; however, if the attempts are unsuccessful, the subject could continue in the study with all the study procedures including vaccination.
- 5) Give the parent / guardian a DC4.
- 6) Arrange an appointment for V05 (D300–390 ± 14 days). Remind the parent / guardian to bring back the DC4 when they return for V05 at a specified date and time.
- 7) Complete the end of study phase CRF of the CRB.
- 8) Complete the source document and the relevant CRFs for this visit.

Visit 5 (180 [± 14] days after Visit 3): Collection of Safety Information, Blood Sample, and Vaccination

Note: V05 can take place up from the day subject turns to 12 months until 15 months of age^a.

- 1) If the DC4 information from Day 0–7 has not yet been obtained, obtain it at this time by interviewing parents. Collet and review the pages of the DC4 with the parent / guardian.
- 2) Obtain significant medical history about the subject.
- 3) Check medications and record reportable ongoing medications. Review temporary contraindications for blood sampling. Ensure the subject has not had any antibiotics within the previous 72 hours (3 days).
- 4) Conduct a physical examination, including, but not limited to, examination of the head (ear, nose, and throat), neck, heart, lungs, abdomen, and extremities. If a routine examination had been performed within the past week by a qualified health care provider, it does not need to be repeated unless there were changes in health status, in which case it may be limited to the affected area.
- 5) Take the subject's temperature. If the temperature is $\geq 38.0^{\circ}\text{C}$ / $\geq 100.4^{\circ}\text{F}$, postpone vaccination until the condition is resolved.
- 6) Contact IRT system for vaccine allocation.

^a “15 months” means the day before the 16th after birth

7) Obtain the blood sample (BL0003 – 6 mL) (see [Section 7.1](#) for detailed instructions regarding the handling of blood samples).

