### **3 Description of the Overall Trial Design and Plan**

#### **3.1 Trial Design**

This will be a Phase II, randomized, active-controlled, observer-blind, age de-escalating, multi-centered study to assess the safety and the immunogenicity of 3 different formulations of an investigational PCV in toddlers (12 to 15 months of age [MoA]), and infants (2 MoA). The vaccine is referred to as SP0202 in what follows.

PSK00008 study is designed to evaluate the safety and immunogenicity of SP0202 formulations in a step-down approach and will involve 2 stages ([Table 3.1](#)):

- In Stage I, toddlers aged between 12 and 15 months, who previously received the 3-dose primary series of Prevnar 13 will receive 1 dose of either one SP0202 formulation (Group 1, 2, and 3) or Prevnar 13 (Group 4), concomitantly administered with Pentacel
- In Stage II, infants aged 2 months will receive 3 doses of either one SP0202 formulation or Prevnar 13 at approximately at 2, 4, and 6 MoA and a 4th dose at 12 to 15 MoA (Groups 5, 6, 7, and 8), co-administered with pediatric vaccines recommended at this age

\* Not applicable from protocol Version 5.0

† Immunogenicity to ENGERIX-B will be presented according to the number of doses received

A total of 140 toddlers (35 participants per group) will be enrolled in Stage I and randomized in a 1:1:1:1 ratio to receive a single dose of either one SP0202 formulation (Groups 1 to Group 3) or Prevnar 13 (Group 4).

A total of 700 infants (175 participants per group) will be enrolled in Stage II and randomized in a 1:1:1:1 ratio to be vaccinated with 1 of the 3 SP0202 formulations (Group 5 to Group 7) or with Prevnar 13 (Group 8) ([Table 3.1](#)).

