Following DMC recommendations after Stage I early safety data review (ESDR), any SP0202 formulation may be excluded from entering Stage II of the study if considered not adequate for further evaluation in infants. In such a case, the number of groups to entered Stage II will be adjusted accordingly and the planned sample size in each selected group will be kept.

An Interactive Response Technology (IRT) will be used to assign participant numbers and study group at each clinical site.

Over the study period of Stage I (Group 1 to 4), toddlers will attend 2 planned visits at D0 and D30. Two blood samples (BL) of 6 mL each will be collected for the assessment of the immunogenicity of the 3 SP0202 formulations, Prevnar 13 and Pentacel: before injection of PCV (BL0001) at D0 (Visit 1 [V01]) and 1 month after PCV injection (BL0002) at D30 (V02).

Over the study period of Stage II (Group 5 to 8), infants will attend 6 planned visits at D0, D60, D120, D150, D300-390, and D330-420. Overall, 3 or 4 BL will be collected for the assessment of the immunogenicity of the 3 SP0202 formulations, Prevnar 13 and pediatric vaccines: before injection of PCV (BL0001; 3 mL) at D0 (V01)\*, 1 month after PCV Dose 3 (BL0002; 6 mL) at D150 (V04), before PCV Dose 4 (BL0003; 6 mL) at D300 (V05), and 1 month after PCV Dose 4 (BL0004; 6 mL) at D330 (V06).

The study vaccine-related immunogenicity assessments will involve both the measurement of serotype specific IgG concentrations and of OPA titers. IgG concentrations for all pneumococcal serotypes included in each of the SP0202 formulations and Prevnar 13 will be measured in all participants. The evaluation of the IgG concentrations will be made using the international standard reference serum 007sp that includes assignment for all serotypes included in SP0202. OPA will be measured in all available samples from Stage 1 and on a subset of Stage 2 samples.

The immunogenicity of the pediatric vaccines administered concomitantly with the study vaccines will be assessed using standard assays for the respective antigens.

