#### 4.2.2.3 Immunogenicity Assessment Methods

##### *Pneumococcal capsular polysaccharide - electro-chemiluminescent assay (PnPS-ECL)*

[figure not shown]

This method will be performed on BL0001 and BL0002 collected from toddlers, and on BL0001\*, BL0002, BL0003, and BL0004 collected from infants.

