#### *Immunogenicity - Stage II infants*

The point estimates and their 95% CI of the following parameters will be presented for each group for each pneumococcal serotype specific IgG concentrations when applicable:

- Percentage of participants with a PD3 and PD4 serotype specific IgG concentrations  $\geq 0.35 \mu\text{g/mL}$
- GM of serotype specific IgG concentrations / titers (pre-dose 1\* as applicable, PD3, pre-dose 4, PD4)

- GM of serotype specific IgG concentrations / titers ratio (PD3/pre-dose 1\* as applicable, PD4/pre-dose 4)

In addition, difference between any SP0202 group (Group 5 to 7) and the Prevnar 13 group (Group 8) and between SP0202 groups will be presented in terms of:

- Differences of percentages of participants with serotype specific IgG concentration  $\geq 0.35 \mu\text{g/mL}$  and 95% CI at PD3
- GM ratio of serotype specific IgG concentrations between groups and 95% CI at PD3 and PD4

Several graphical representations will be used such as: RCDCs of individual concentrations, Boxplots of the  $\log_{10}$  concentrations and Forest plots of GMCs for all serotypes.

\*Pre-dose 1 BL is done only for participants enrolled before protocol amendment V5.0

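### Infant rescue with Prevnar 13 depends on the PD3 result alone, so an SP0202 infant low at PD4 who was adequate at PD3, or has no PD3 result, gets no recommendation

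*SAP*

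**What the plan says.** The rescue rule is in SAP 3.2 (Trial Plan, Vaccination), below Table 3.2. It covers SP0202 recipients only. It recommends one Prevnar 13 dose, given outside the study visits, when IgG is below 0.35 µg/mL for enough of the shared serotypes.

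- Toddlers: "4 or more serotypes in common between SP0202 vaccine and Prevnar 13 at 1-month post-vaccination".
- Infants: "4 or more serotypes in common between SP0202 vaccine and Prevnar 13 at 1-month post-dose 3".
- Timing of the infant dose: "as soon as possible after the immunogenicity results of the fourth dose of SP0202 vaccine for infants".

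The rule has no criterion based on the PD4 result and no provision for a missing PD3 result. Nothing else in the supplied text of either document adds one.

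Three other places bear on this:

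- Protocol 5.1.4 (infants, Visit 4) provides for a repeat attempt at a failed blood draw, and then says that "if the attempts are unsuccessful, the subject could continue in the study with all the study procedures including vaccination".
- SAP 4.2.2.3 already plans the pneumococcal IgG assay on "BL0002, BL0003, and BL0004 collected from infants", and BL0004 is the PD4 sample.
- SAP 5.1.1.2 already applies the 0.35 µg/mL cut-off at both time points: "Percentage of participants with a PD3 and PD4 serotype specific IgG concentrations".

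**The concern.** The rescue dose is there for children who received SP0202 and did not respond adequately to serotypes that Prevnar 13 would have covered. For infants, the decision uses a sample taken before Dose 4, but the dose is given once the result after Dose 4 is known. Two kinds of infant then have a low result on file and no recommendation:

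- (a) fewer than 4 shared serotypes low at PD3, but 4 or more low at PD4;
- (b) no PD3 result, and 4 or more low at PD4.

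Both have completed four SP0202 doses and have had no Prevnar 13 in the study. What is at stake is the protection of these participants. Endpoints, analysis sets and sample size are not involved.

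**Working it through.** **Planned numbers (SAP 5.5).** The evaluable numbers per group reproduce:

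- toddlers: 35 × 0.90 = 31.5, stated as 31;
- infants at PD3: 175 × 0.80 = 140;
- infants at PD4: 175 × 0.70 = 122.5, stated as 122.

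Over the three SP0202 infant groups, 3 × 175 = 525 are randomized, 3 × 140 = 420 are evaluable at PD3 and 3 × 122 = 366 at PD4.

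**The rule applied to each pattern** (low means below 0.35 µg/mL for 4 or more of the 13 shared serotypes):

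| PD3 | PD4 | Recommendation under SAP 3.2 |
|---|---|---|
| low | low | yes |
| low | adequate | yes |
| low | no result | yes, but no date, because the timing depends on a Dose 4 result |
| adequate | low | none: case (a) |
| no result | low | none: case (b) |

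Case (b) can arise because Protocol 5.1.4 lets a child with a failed V04 draw continue, and SAP 5.3.2 does not impute missing results.

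**Age of the deciding value.** SAP 3.1 says that "infants will attend 6 planned visits at D0, D60, D120, D150, D300-390, and D330-420". PD3 is drawn at D150 (V04), Dose 4 is given at D300-390 (V05) and PD4 is drawn at D330-420 (V06).

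- PD3 sample to Dose 4: 300 − 150 = 150 days, up to 390 − 150 = 240 days.
- PD3 sample to PD4 sample: 330 − 150 = 180 days, up to 420 − 150 = 270 days.

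**How many infants.** The documents do not give the share low at either time point, so this shows scale only and is not an estimate.

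- Each 1% of the 366 SP0202 infants evaluable at PD4 is 3.7 infants.
- Assume each of the 13 serotypes is below 0.35 µg/mL at PD4 independently with probability q. The expected number low is then 366 × P(X ≥ 4), with X binomial (13, q). For q = 2%, 5%, 10% and 20% the probability is 0.0001, 0.0031, 0.0342 and 0.2527, which gives about 0.04, 1.1, 12.5 and 92 infants. Cases (a) and (b) are only part of these, since infants also low at PD3 are already covered. Responses within a child may well be correlated, which would change the figures.
- For case (b), assume 1% to 10% of the 366 have no PD3 result: 3.7 to 36.6 infants. The arithmetic ceiling is 525 − 420 = 105, but the SAP describes that loss as drop-out, and most drop-outs would not reach V06. With 10% missing, 36.6 × 0.0342 = 1.3 infants would be low at PD4 if q = 10%, and 36.6 × 0.2527 = 9.2 if q = 20%.

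**Date for infants without PD4.** The V06 window closes at V05 + 30 + 14 = V05 + 44 days.

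**The case against.** The best defence is that deciding on PD3 and dosing after PD4 is coherent. A reader might infer that waiting for the Dose 4 results makes sense only if those results decide. The documents do not support that. PD4 IgG is a primary objective (SAP 2.1). Protocol 5.2.5 rules out vaccines from outside the study through Visit 6, apart from influenza and COVID-19 vaccines. A prohibited vaccine in the booster phase removes a child from PPAS3 (SAP 5.2.1). A rescue dose before V06 would disturb all of this. No reason for the wait is stated, but this one is sufficient. PD3 is also the time point of the listed infant endpoint for the 0.35 µg/mL cut-off (SAP 4.2.1). This defence stands as a reason to defer the dose and to keep PD3 as a trigger. It gives no reason to disregard a low PD4 result once it is available.

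A reader might also see a fault in recommending rescue to an infant low at PD3 but adequate at PD4. That is a defensible cautious choice for a child who failed the primary series without Prevnar 13. Deciding on the latest result alone would withdraw cover from these infants.

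The toddler rule invites a direct comparison, since toddlers "who previously received the 3-dose primary series of Prevnar 13 will receive 1 dose of either one SP0202 formulation" and are judged one month after that fourth PCV dose. The parallel holds for dose number and age only. Toddlers have three earlier Prevnar 13 doses and a single post-dose study sample, so their rule had no other time point to use.

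Finally, the number affected is not shown to be large. Case (a) needs at least 10 of 13 shared serotypes adequate at PD3 and then 4 or more low a month after a further dose. Case (b) needs a failed draw despite the repeat attempt. This stands, and it limits the weight of the point.

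**Conclusion.** The gap is real and worth closing as a cheap improvement. Under SAP 3.2 as written, an SP0202 infant low for 4 or more shared serotypes at PD4 gets no recommendation if PD3 was adequate or missing, although the result is in hand when the rule is acted on. The number of such infants is unknown and probably small.

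A reader might infer that these infants are denied a dose. The text does not go that far: it makes no recommendation for them, and it does not forbid vaccination outside the study. Nor is any immunogenicity or safety analysis affected.

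The conclusion assumes that SAP 3.2 states the whole rule. The supplied protocol text does not carry it, but parts are redacted and the Operating Guidelines are not available, so that absence is not counted as an error. If site-facing text already includes a PD4 trigger, only the SAP wording needs aligning.

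**What to change.** In the infant criterion of SAP 3.2, change the time point to *1-month post-dose 3 or 1-month post-dose 4*. Keep the threshold, the count of 4 serotypes and the stated timing. Add one sentence: for an infant low at PD3 with no PD4 result, issue the recommendation when the V06 window closes (V05 + 44 days) or at withdrawal. Make the same change wherever the rule is given to sites.

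This removes no infant now covered and closes cases (a) and (b). It needs no new sample or assay, and endpoints, analysis sets and sample size stay as they are. The downside is possibly a few more recommended Prevnar 13 doses. Because only SP0202 recipients are eligible, each recommendation also reveals that the child received SP0202. The present rule already does this, but for an infant without PD4 it could now happen before the safety call at V05 + 180 days.

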### ***Blood sampling***

During Stage I, all toddlers will provide 2 BL of 6 mL each for the assessment of the immunogenicity of the 3 SP0202 formulations, Prevnar 13 and Pentacel: a first sample (BL0001) before injection at D0 (V01) and a second sample (BL0002) at D30 (+14 days) post-injection (V02).

During Stage II, all infants will provide 3 or 4 blood samples for the assessment of the immunogenicity of the 3 SP0202 formulations, Prevnar 13 and pediatric vaccines: a sample before injection of PCV (BL0001; 3 mL) at D0 (V01)\*, a sample 1 month after PCV Dose 3 (BL0002; 6 mL) at D150 ( $\pm$  14 days; V04), before PCV Dose 4 (BL0003; 6 mL) at D300-390 ( $\pm$ 14 days; V05), and 1 month after PCV Dose 4 (BL0004; 6 mL) at D330-420 (+ 14 days; V06).

Immunogenicity of pneumococcal antigens will be assessed in priority versus concomitants antigens.

### ***Safety***

Reactogenicity data will be collected in all participants after each injection. Solicited injection site reactions will be collected for both study and concomitant pediatric vaccines.

All participants will be observed for 30 minutes after vaccination, and clinical site personnel will record any unsolicited systemic AEs occurring during that time as immediate unsolicited systemic AEs in the (electronic) case report book (CRB).

Participants' parents / guardians will record in the DC / eDC information about AEs (solicited and unsolicited), concomitant medications, and any medical visits or hospitalizations.

Solicited injection site and systemic reactions will be collected from D0 to D7 following injection. Unsolicited events will be collected from D0 to D30 following injection. SAEs and AESIs will be collected throughout the study (from D0 until the 6-month follow-up safety phone contact).

---

\* Not applicable from protocol Version 5.0

For both toddlers and infants, anaphylaxis/hypersensitivity, convulsions (including febrile convulsions), hypotonic-hyporesponsive episode, and apnea will be considered as AESIs.

**Table 3.3: Table of Study Procedures 1 (Toddlers)**

Phase II Trial, 2 Visits, 2 Phone Calls, 1 dose of either one SP0202 formulation or Prevnar 13, along with 1 concomitant dose of Pentacel, 2 Blood Samples, approximately 6-month duration per participant

Visit/Contact	V01	PC1	V02	PC2 6-month safety follow-up
Trial timelines (approximate # of days [D])	D0	D8	D30	D180
Visit intervals		V01 + 8 D	V01 + 30 D	V01 + 6 months
Time windows (days)		+2	+14	+14
Informed consent	X			
Inclusion/exclusion criteria	X			
Collection of demographic data	X			
Medical history	X			
Physical examination and temperature*	X		X	
Randomization/allocation of participant number	X			
Blood sampling (BL), approximately 6 mL†	BL0001		BL0002	
Injection (SP0202 or Prevnar 13)	X			
Injection (pediatric vaccine [Pentacel])	X			
30-Minute observation period	X			
Diary card (DC) / electronic DC (eDC) provided collected	DC1/eDC1		DC1/eDC1	
Memory aid (MA) provided checked			X	X
Telephone contacts		X‡		X**
Injection Site Reactions & Systemic Events Assessment§			X	
Collection of reportable concomitant medications	X		X	
Trial termination record			X	
Collection of SAEs and AESIs	To be reported at any time during the trial			

\* Mandatory at injection Visit (before injection). For V02: physical examination and temperature measurement will be performed, if necessary, based on the health status of the participant.

† BL0001 is to be collected prior to any injection (SP0202, Prevnar 13, and Pentacel).

‡ During this call the staff will determine whether the participant experienced any SAE and AESI not yet reported. The site staff will remind participant's parent / guardian to continue using the DC / eDC.

§ Solicited injection site and systemic reactions will be collected for 7 days after injection. Unsolicited AEs will be collected for 30 days after injection.

**\*\*** During this call the staff will review the MA with the participant's parent / guardian and determine whether the participant experienced any SAE or AESI not yet reported.

